**PSIY-511-15: Adapting and Evaluating Dialectical Behaviour Group Therapy
for Adults with Dual Diagnosis (Intellectual Disabilities with Psychiatric
Disorder)**

NCT02919826

4 Dec 2017

Study Protocol & Statistical Analysis

Present study

The present study is a pilot community-based, double blind, randomized controlled trial of an adapted DBT skills group and program for individuals with Intellectual and Developmental Disabilities (IDD) and psychiatric illness. The purpose of this study was to clinically evaluate and empirically determine the feasibility and effectiveness of delivering an adapted DBT community-based skills group to adults with intellectual disability and transdiagnoses. Dykstra and Charlton's work, *Dialectical Behavior Therapy Skills Training: Adapted for Special Populations* (DBT-SP; written in 2004 and revised in 2008; Dykstra & Charlton, 2008, Charlton & Dykstra, 2011), was the basis from which the adapted DBT manual and program (i.e. aDBT-ID) was used in the present study. As part of a community based DBT program, in addition to the manualized skills group, other components included mental health treatment i.e. psychiatric medication and consultation, individual therapy, crisis services, caregiver coaching and team consultation for both the researchers and clinicians.

Methods

Participants

A community based sample of 19 adults with mild to moderate IDD and transdiagnoses i.e. co-morbid psychiatric disorders participated in the present study. Inclusion criteria were: age 18-65 years old, administratively confirmed diagnosis of mild to moderate IDD, co-morbid psychiatric diagnoses and history of emotional and behavioural concerns and lead agency commitment i.e. allocated caregiver to attend all sessions. Exclusion criteria included a diagnosis of autism spectrum disorder or acute psychosis interfering with daily functioning.

The group participants comprised of 9 males and 10 females; ages ranging from 22 to 34 with one 52 year old. All were referred with confirmed diagnoses of mild (16) to moderate (3) IDD established by their administrative eligibility for support services i.e. DSM-V criteria for IDD. All lived in either residential treatment homes (3), group homes (5), host family home (2) or independent living either alone (4) with a roommate (2), with their parents (2) or a spouse (1).

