Co-morbid psychiatric diagnoses upon referral (not mutually exclusive) included Personality Disorders (BPD 10, Mixed PD 2), Mood Disorders (Depression 2, Anxiety 8, Bi-Polar 3, OCD 2), Psychotic Disorders (2), Childhood Disorders (ADHD/ADD 7), Trauma Disorders (PTSD 4), Substance Abuse Disorder (1), Sexually Problematic Behaviour/Pedophilia (2), Acquired Brain Injury (1), Seizure Disorder (2) and Speech and Language Disorder (1). All participants were identified as having significant problems with emotional dysregulation and chronic interpersonal difficulties with family, friends and caregivers. In addition, the majority

were experiencing behavioural difficulties with anger that impacted their daily functioning. All participants had a medication regime including a range of psychotropic medications for behavioural control and mental health stability (e.g. anti-psychotics, anti-depressants, anti-anxiety, mood stabilizers) and treatments for associated physical health conditions (anti-convulsants, diabetes medication).

Clinical services outside of the group included psychiatric medication oversight for all participants except four who had family physicians prescribing. All participants had regular therapy or treatment interventions with either assigned social workers, psychologists, behaviour therapists, nurse or addiction counsellors. Also, participants had a variety of tertiary care team involvement including specialization in either dual diagnosis, mental health crisis, assertive community treatment and 24 hour access to mental health crisis lines. Some participants had regular legal oversight from either court diversion workers or probation officers.

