Participants and caregivers were then de-identified and randomly assigned utilizing a relevant software (Randomizer.org; or “Research Randomizer”) with the researcher blind to group identities. Randomization occurred once a dozen participants were recruited and then again prior to the second group to accommodate rolling recruitment. Participants were initially allocated to either the treatment group or waitlist control group for one of the three sequential groups. All participants attended their assigned group except for one who requested an earlier group due to travel limitations and one replacement for the last group following client attrition.

Measures

Participation in the aDBT-ID trial was initiated by recruitment letters and by convenience sampling through partnering agencies. Referrals were initially screened for eligibility criteria e.g. level of ID and ASD, and availability of both client and caregiver for the trial and time commitment required for group randomization and attendance. Upon referral and consent by both client and caregiver, an interview was conducted by a research assistant (independent from the research team and blind to the group allocation) who confirmed eligibility and obtained written consent. The interview was completed prior to randomization to one of the three groups, and one month prior to group commencement. The interview included a demo-graphic questionnaire which included information on age, gender, locality, living arrangements, affiliated agency, caregiver role and experience, diagnoses, medications, and existing clinical services and supports.

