Following group treatment, interviews and post assessments were conducted by independent research assistants, with both participants and caregivers, within approximately four weeks of group completion. In addition to re-administered assessments to measure potential change, the post-interview included an update and feedback questionnaire that focused on their qualitative experiences participating in the group, what they learned, whether they believed the skills presented would benefit their daily lives, coping strategies that they were currently utilizing, and feedback regarding suggested changes to the group. They were also asked about any significant changes in their circumstances since their group attendance (e.g. residential moves, hospitalizations, or legal charges) to illustrate possible contributory attrition factors if applicable. Also administered was an adapted multiple choice questionnaire, the Global Impression of Change: aDBT-ID. The measure was adapted from the Patients Global Impression of Change Scale (Hurst & Bolten, 2004) and then reviewed with the research team for face validity. The questionnaire identified the initial presenting problems and then measured both client and caregiver perspectives of overall change following the group, and for each respective module; with five responses ranging from no change to significant change. Accordingly, the interviews with the caregivers matched the clients' post assessment with the psychometric measures, feedback interview and GIC questionnaire.

Statistical Analysis

Outcomes for the group were evaluated using both quantitative and qualitative measures in order to identify any group treatment changes; but also to assess the experiences by both clients and caregivers in the treatment process and their views on participation in community-based research. Given the small sample group and attempts at research rigour, quantitative measures were analysed utilizing an 'intent to treat' paradigm such that all participants who started the group were included in analysis. Using a mixed method ANOVA within SPSS v24, group differences, within and between, were assessed using non-parametric analysis due to group composition i.e. Wilcoxon signed-rank and Man-Whitney U tests, respectively.

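### The plan names a mixed ANOVA but describes separate Wilcoxon and Mann-Whitney tests, and specifies no between-arm contrast of change, so uncontrolled pre-post change could be read as effectiveness

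*Combined protocol and SAP*

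**What the plan says.** The Present study section describes a "pilot community-based, double blind, randomized controlled trial of an adapted DBT skills group and program", with the aim to "empirically determine the feasibility and effectiveness of delivering an adapted DBT community-based skills group". Under Procedure the comparator is a waitlist: "Participants were initially allocated to either the treatment group or waitlist control group for one of the three sequential groups". Arm sizes and the allocation ratio are not given.

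The Statistical Analysis section has one sentence on inference: "Using a mixed method ANOVA within SPSS v24, group differences, within and between, were assessed using non-parametric analysis due to group composition", completed by "Wilcoxon signed-rank and Man-Whitney U tests, respectively". Within is therefore Wilcoxon and between is Mann-Whitney. The same section presents the quantitative measures as a way to find change due to the group. It does not say which of the two tests carries the conclusion.

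On timing, the Measures section says of the baseline interview: "The interview was completed prior to randomization to one of the three groups, and one month prior to group commencement". Of follow-up it says: "Following group treatment, interviews and post assessments were conducted by independent research assistants, with both participants and caregivers, within approximately four weeks of group completion". No separate assessment of waitlist participants at the end of their wait is described.

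**The concern.** In a two-arm, pre-post design, a mixed ANOVA expresses the treatment effect as the group-by-time interaction. A Wilcoxon and Mann-Whitney pair has no such term. The signed-rank test asks only whether scores moved in one set of people. The Mann-Whitney test compares arms, but the plan does not say whether on post scores or on change. Both named methods cannot be the analysis.

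Movement without any effect of the group is plausible here. Under Participants, "All participants were identified as having significant problems with emotional dysregulation and chronic interpersonal difficulties", so some regression to the mean is possible. All participants also had medication and regular therapy or other treatment outside the group. A control arm is there to remove such drift, and a within-arm test does not use it. If a significant pre-post result, or significance in one arm but not the other, were taken as evidence, the effectiveness statement would rest on something that is not a test of treatment.

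**Working it through.** **No plan figure to reproduce.** The documents give no power, alpha, effect size or SD. The one relevant sum is 19 - 1 = 18 analysed, which agrees with the stated sample.

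**Assumptions, none from the documents.** Two-sided 0.05; normal change scores; no treatment effect; the same drift d in everyone, in SDs of the change score; exact tests; arms of 6 v 12, 9 v 9 or 12 v 6 (treated v waitlist), each summing to 18.

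**Wilcoxon in one arm of 6.** The smallest two-sided p-value is 2/64 = 0.031 and the next is 4/64 = 0.063, so the test rejects only when all six changes share a sign:

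P = Φ(d)^6 + Φ(-d)^6

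- d = 0.2: 0.579^6 + 0.421^6 = 0.038 + 0.006 = 0.043
- d = 0.8: 0.788^6 + 0.212^6 = 0.240 + 0.000 = 0.240

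For n = 9, 12 and 18 the rejection rates were simulated (200,000 trials per cell).

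**Treated significant, waitlist not.** The arms are independent, so this has probability p_T × (1 - p_W). For example, at d = 0.5 with 9 v 9: 0.218 × (1 - 0.218) = 0.171.

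False rejection, %:

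| Drift (SD of change) | Wilcoxon n=6 | n=9 | n=12 | Pooled 18 | One-arm pattern 6 v 12 | 9 v 9 | 12 v 6 |
|---|---|---|---|---|---|---|---|
| 0.2 | 4.3 | 6.6 | 8.3 | 12.0 | 4.0 | 6.1 | 8.0 |
| 0.3 | 5.9 | 10.1 | 13.6 | 21.2 | 5.1 | 9.1 | 12.8 |
| 0.5 | 11.0 | 21.8 | 31.3 | 49.6 | 7.6 | 17.1 | 27.9 |
| 0.8 | 24.0 | 49.1 | 66.6 | 87.5 | 8.0 | 25.0 | 50.7 |

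The plan does not say that all 18 are pooled; that column shows what happens if they are.

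**Direct test.** A shift common to both arms cancels in a Mann-Whitney test on change, so its false-positive rate does not depend on d. It is 4.0% at 9 v 9 and 4.2% at 6 v 12 or 12 v 6.

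**Precision of the direct contrast at 9 v 9.** With pre-post correlation ρ, the SD of change is sqrt(2(1 - ρ)) in units of the raw-score SD: 1.00 at ρ = 0.5 and 0.775 at ρ = 0.7 (both assumed). The difference detectable with 80% power is (1.96 + 0.84) × SD × sqrt(2/9), which is 1.32 and 1.02 raw-score SDs. The 95% interval half-width is about 2.12 × SD × sqrt(2/9), which is 1.00 and 0.77.

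**The case against.** The plan does include a between-group test. A reader might infer from the missing interaction that the treatment effect is never tested, and the documents do not support that. Mann-Whitney on change would test group-by-time, and on post scores it would be a valid randomized comparison that ignores baseline. What stands is that neither is specified.

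A reader might also infer that pre-post significance carries the effectiveness claim, that all 18 are pooled, or that one arm's p-value is set against the other's. The text says none of these; it lists two tests and leaves their roles open.

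Nor is the error rate of the one-arm pattern always far above 5%. With 6 treated and 12 waiting it is only 4-8%. The Procedure section has randomization starting at a dozen participants and three sequential groups, so a small treated arm is at least as plausible as a large one.

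The drift itself is assumed. Eligibility has no score threshold, and the interpersonal difficulties are called chronic, so regression to the mean may be modest.

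Finally, in a pilot of 18 the correct contrast has little power. That is true. It argues for an estimate with an interval, and gives no reason to let pre-post p-values stand in for it.

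**Conclusion.** The concern holds as a defect of specification. The only inferential sentence names two incompatible analyses. The between-arm contrast that would express effectiveness is not defined, and nothing stops within-group change from being read as effect.

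The size depends on arm sizes and drift that the documents do not give. Over the assumed range, a treated-arm Wilcoxon test misleads in anything from about 4% of null trials (6 treated, 0.2 SD) to 67% (12 treated, 0.8 SD), against about 4% for the direct test. In no part of this range does the within-arm test separate treatment from drift.

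The timing of assessment matters as much as the choice of test. The only post-assessment described follows group treatment. If waitlist participants were measured again only after their own group, both arms had been treated by then, and no test on those scores isolates the effect. The documents do not show that an end-of-wait assessment was omitted; they only describe none.

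**What to change.** 1. Delete the mixed-ANOVA wording and name one effectiveness analysis: the between-arm difference in baseline-adjusted post score on each scale, or at minimum a Mann-Whitney test on change. Compare participants by randomized arm and report an estimate with a confidence interval.
2. State that the waitlist scores used were taken before those participants received the group, and say when. If no such assessment exists, state that the trial gives no controlled estimate of effectiveness, and report only pre-post change and feasibility.
3. Label the Wilcoxon results descriptive. State that they, and any contrast of one arm's p-value with the other's, are not evidence of a treatment effect.

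The cost goes beyond wording. The document is written in the past tense with an analysed sample of 18, so a small re-analysis is needed. Pre-post results lose their standing as effectiveness evidence. The direct contrast will be imprecise, with a half-width of roughly 0.8 to 1.0 raw-score SD under the assumptions above. If end-of-wait scores were not collected, rewording cannot supply them.

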After the questionnaire, a two part assessment involving an interview and psychometric measures was conducted. The interview conducted with clients to identify insight into their own emotional and behavioural difficulties, and their motivation to gain coping skills with these difficulties. Caregivers were also interviewed about their perspectives of the client’s overall profile and need for treatment. The second part included a battery of both psychometric and observational measures to gather baseline measures of client emotional regulation, anger control and psychopathology. Standardized measures included the Difficulties in Emotional Regulation Scale (Gratz & Roemner, 2004), Novaco Anger Scale: Provocation Inventory (Novaco, 2003), and Reiss Scale of Dual Diagnosis (Reiss, 1990), respectively. The caregiver interview aimed to identify what they perceived the presenting problems to be, the effect of the issue(s), how they addressed the issue with the participant, and coping strategies currently utilized. The matched caregiver pre-assessment measures included the Emotion Regulation Checklist (Cicchetti & Shields, 1997; adapted with written permission by Cicchetti, 2016), Novaco Anger Scale: Provocation Inventory (Novaco, 2003) and Reiss Scale of Dual Diagnosis (Reiss, 1990). Measures were completed in relation to caregiver perspectives of clients’ profiles of emotional regulation, anger control and mental health difficulties. The psychometric measures noted above all have robust validity indices as noted in their respective manuals.

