Qualitative measures were evaluated using thematic analysis (Braun & Clarke, 2006) for both client and caregiver interviews to identify and illustrate thematic patterns through an iterative process of data immersion, category generation and theme identification followed by inter-rater verification.

Post-assessment data was unable to be obtained for one participant and one caregiver, and as such both qualitative and quantitate components were conducted with a sample size of N=18.

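### The between-group Mann-Whitney test has no stated outcome variable and no baseline adjustment, although the scales are measured at baseline; a baseline-adjusted comparison would be more powerful

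*Combined protocol and SAP*

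**What the plan says.** The Measures section describes, before randomization, "a battery of both psychometric and observational measures to gather baseline measures of client emotional regulation, anger control and psychopathology". Clients complete scales of emotion regulation, anger and psychopathology, and caregivers complete a matched set. After the group the same scales are repeated: "In addition to re-administered assessments to measure potential change". The Global Impression of Change questionnaire is described only at the post-assessment, so it has no baseline.

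The Statistical Analysis section then states: "Using a mixed method ANOVA within SPSS v24, group differences, within and between, were assessed using non-parametric analysis due to group composition". The two procedures that it goes on to name are given as "i.e. Wilcoxon signed-rank and Man-Whitney U tests, respectively". So Wilcoxon serves the within-group question and Mann-Whitney the between-group question. No covariate is named, and the variable entered in the Mann-Whitney test is not given. The last paragraph of the section reports that "both qualitative and quantitate components were conducted with a sample size of N=18".

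**The concern.** Only the randomized treatment-versus-waitlist contrast can speak to effectiveness, which is part of the stated purpose. With so few people, how that contrast is tested matters more than usual.

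A Mann-Whitney test on post scores makes no use of the baseline. The same test on change scores does use it, but gives it a fixed weight of one, whatever the pre-post correlation. Adjustment for baseline estimates the weight from the data. The plan already holds the baseline scores, so an unadjusted test gives up precision that costs almost nothing to recover.

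Leaving the variable unnamed is a second problem. Post and change scores can lead to different answers on the same data, so a reader cannot tell which comparison was run.

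**Working it through.** **What the plan gives.** There is no power calculation to reproduce. The documents give 19 participants, 18 analysed, and allocation to treatment or waitlist over three sequential groups. They give no arm sizes, alpha, effect size, SD or correlation.

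**Assumptions.** Two-sided alpha 0.05; N = 18 split 9 v 9 (6 v 12 as a check); a true effect of 1 SD; bivariate normal baseline and post scores; pre-post correlation rho from 0.4 to 0.7.

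**Step 1: precision.** Relative to a post-score comparison, the variance factor is 1 for post scores, 2(1 − rho) for change scores and 1 − rho² for baseline adjustment.
- rho 0.4: 1.00, 2(0.6) = 1.20, 1 − 0.16 = 0.84
- rho 0.5: 1.00, 2(0.5) = 1.00, 1 − 0.25 = 0.75
- rho 0.7: 1.00, 2(0.3) = 0.60, 1 − 0.49 = 0.51

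Adjustment has the smallest variance in each case.

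**Step 2: power.** Simulated trials, 9 v 9, with the exact Mann-Whitney test and the ANCOVA t-test:

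| rho | Mann-Whitney, post | Mann-Whitney, change | ANCOVA |
|---|---|---|---|
| 0.4 | 45% | 38% | 55% |
| 0.5 | 45% | 45% | 60% |
| 0.7 | 45% | 67% | 76% |

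At 6 v 12 and rho 0.7 the figures are about 41%, 62% and 72%.

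Some of the gap is test size, not adjustment. The exact Mann-Whitney test runs at about 4% and ANCOVA at 5%. At rho 0, where adjustment cannot help, ANCOVA is already 3 to 4 points ahead (48% v 45%). Held to the same size, ANCOVA at rho 0.5 has 56% power instead of 60%.

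Rank ANCOVA (9 v 9) gives about 57% at rho 0.5 and about 70% at rho 0.7. At rho 0.8 it gives 82%, against 84% for Mann-Whitney on change scores and 89% for ANCOVA.

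**Step 3: chance imbalance.** The SD of the between-arm baseline difference, in baseline SDs, is √(1/9 + 1/9) = 0.47 at 9 v 9 and √(1/6 + 1/12) = 0.50 at 6 v 12.
- Gap above 0.5 SD: 2[1 − Φ(0.5/0.471)] = 29% at 9 v 9; 2[1 − Φ(0.5/0.5)] = 32% at 6 v 12.
- Gap above 1 SD at 9 v 9: 2[1 − Φ(1/0.471)] = 3.4%.

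**Step 4: error rate given the gap** (9 v 9, no treatment effect):
- Gap of exactly 0.5 SD, rho 0.4 to 0.7: Mann-Whitney about 4% on post or change scores. There is no inflation.
- Gap of exactly 1 SD, rho 0.7: 18% (post), about 8% (change), 5% (ANCOVA).
- Averaged over all gaps above 0.5 SD: post scores 7.2% at rho 0.5 and 9.6% at rho 0.7; change scores 7.5% and 5.9%; ANCOVA about 5%. Since a 0.5 SD gap shows no inflation, this excess comes from the larger gaps.
- Averaged over all randomizations: Mann-Whitney about 4%.

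**The case against.** **The plan may already use the baseline.** The sentence opens with a mixed ANOVA, and the scales were repeated to look for change. With two time points, the group-by-time test of a mixed ANOVA is a comparison of change scores. A reader might infer that the plan discards its baseline data; the documents do not establish that. What stands is narrower: the variable is unnamed, and the same sentence hands the analysis to tests with no covariate. The ANOVA wording therefore supplies no adjustment. ANCOVA has more power than either Mann-Whitney version at each correlation shown.

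**Randomization already deals with imbalance.** On average it does. A reader might infer from the 29-32% frequency of half-SD gaps that the test is often misleading. It is not: the error rate at such a gap is about 4%, and the 18% figure belongs to a gap that only about 3% of 9 v 9 randomizations reach. The case for adjustment rests mainly on power.

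**The simulation favours ANCOVA.** Scores are normal by construction, whereas the authors chose non-parametric tests because of group composition. This is a fair limit on the size of the gain. A permutation p-value answers the worry about the null distribution, but not the dependence of the power figures on normality.

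**The contrast itself is not defined.** The Measures section places post-assessment after group completion and describes no assessment during the waitlist period. It would be wrong to read 18 as the size of the treatment-versus-waitlist comparison, or nine per arm as fact. For caregivers, the Participants section says only 14 completed assessments. This objection stands: adjustment can help only where concurrent randomized outcomes exist.

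**Conclusion.** The point holds as one of efficiency and specification. The between-group test is valid on average, but its variable is unstated and no baseline adjustment is specified.

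Under the assumptions above, ANCOVA's advantage over Mann-Whitney on post scores is 10 points of power at rho 0.4 (55 − 45), 15 at 0.5 (60 − 45) and 31 at 0.7 (76 − 45). Against change scores it is 17 (55 − 38), 15 (60 − 45) and 9 (76 − 67). A few points of each gap reflect the conservative exact test. These sizes depend on a correlation, effect and split that the documents do not give.

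Protection against chance imbalance is a secondary benefit, confined to large and uncommon gaps. Nothing here shows that the planned test is biased or that its overall type I error is inflated.

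**What to change.** In the Statistical Analysis section:

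1. Define the between-arm contrast, and state which treatment and waitlist post scores the trial holds for it.
2. For each scale with a baseline, make the primary between-arm analysis an ANCOVA of post score on randomized arm plus the same scale's baseline score. Report the adjusted difference with a 95% CI.
3. Take the p-value from a permutation test that re-randomizes the arm label within each randomization batch. The Procedure section describes randomization at a dozen recruits and again before the second group, so free permutation across everyone would not match the design. State how the participant who moved group on request and the one replacement are handled.
4. Keep the Mann-Whitney test as a sensitivity analysis and say whether it compares post or change scores. Remove or explain the mixed ANOVA wording.

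Rank ANCOVA is usable if a rank method is preferred, but it is less powerful than ANCOVA and not an equivalent.

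The cost is one degree of freedom per scale and a few sentences of text, with no new data collection. The section is written in the past tense, so if the analysis is added after the data were seen it must be labelled post hoc.
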